3.3 Safety Variables

Safety and tolerability will be assessed in terms of AEs (including SAEs), deaths, laboratory data, vital signs, ECGs, and exposure. These will be collected for all patients. For physical examination, only information on whether the assessment was performed or not is recorded, and any abnormal findings are reported as either medical history or AEs.

Safety data will be summarized from the ‘On-treatment’ period, unless otherwise specified. ‘On-treatment’ is defined as assessments between the date/time of start of study treatment (i.e. durvalumab/placebo) and 90 days following discontinuation of study treatment (i.e. the last dose of durvalumab/placebo), or up to and including the date of initiation of the first subsequent anti-cancer therapy (including radiotherapy, except for palliative radiotherapy), whichever occurs first.

3.3.1 Study Treatments

Study treatment in this study refers to durvalumab or placebo. Study treatments are described in [Table 4](#). Exposure will be defined for durvalumab and placebo regimens.

Table 4 Study Treatments

Study treatment name	Route of administration	Dosing instructions
Durvalumab	IV	1500 mg infusion over 60 min q4w.
Placebo	IV	Infusion over 60 min q4w.

IV Intravenous; min Minutes; q4w Every 4 weeks.

3.3.2 Exposure and Dose Interruptions

Exposure (i.e. duration of treatment) will be defined as follows:

- Total (or intended) exposure of study treatment
 - Total (or intended) exposure = min (last dose date where dose > 0mg + 27 days, date of death, date of DCO) – first dose date +1 day
- Actual exposure of study treatment
 - Actual exposure = intended exposure – total duration of dose interruptions and cycle delays
- Calculation of duration of dose delays/interruptions (for actual exposure)

- Duration of dose delays/interruptions = sum of positive values of [date of the dose – date of previous dose – (28 + 3) days], where records corresponding to either a dose interruption or a dose delay are identified based on eCRF item “Action taken, study drug”=“Dose interruption” as collected in the Exposure eCRF form.

Dose reductions of durvalumab/placebo are not permitted, and the actual exposure calculation makes no adjustment for any dose reductions that may have occurred.

Number of treatment cycles received

Exposure will also be measured by the number of cycles received. A cycle corresponds to a period of one dose of treatment (28 days). If a cycle is prolonged due to toxicity, this should still be counted as one cycle. A cycle will be counted if treatment is started even if the full dose is not delivered.

Patients who permanently discontinue during a dose delay

If a decision is made to permanently discontinue study treatment (i.e. durvalumab/placebo) in-between cycles or during a dose delay then the date of last administration of study medication recorded will be used in the calculation of exposure.

3.3.3 Dose Intensity

Relative dose intensity (RDI) is the percentage of the actual dose delivered relative to the intended dose through to treatment discontinuation. RDI will be defined as follows:

- $RDI = 100\% \times d/D$, where d is the actual cumulative dose delivered up to the actual last day of dosing and D is the intended cumulative dose up to the actual last day of dosing. D is the total dose that would be delivered, if there were no modification to dose or schedule. When accounting for the calculation of intended cumulative dose 3 days should be added to the date of last dose to reflect the protocol allowed window for dosing.

When deriving actual dose administered the volume before and after infusion will also be considered.

3.3.4 Adverse Events

Adverse events and SAEs will be collected throughout the study. SAEs will be collected following signature of the first informed consent [ICF1] and following signature of the second informed consent for the observation period [ICF2b], and all SAEs and AEs will be collected following signature of the second informed consent for the treatment period [ICF2a) until 90 days after the last dose of study treatment (durvalumab/placebo). A treatment-emergent

adverse event (TEAE) is defined as an AE with an onset date, or a pre-existing AE worsening (by Investigator report of a change in intensity), during the ‘on-treatment’ period as defined in Section 3.3. The Medical Dictionary for Regulatory Activities (using the latest or current MedDRA version) will be used to code the AEs. Adverse events will be graded according to the National Cancer Institute (NCI) Common Terminology Criteria for Adverse Event (CTCAE) version 5.0.

Adverse Events of Special Interest and Adverse Events of Possible Interest

Some clinical concepts (including some selected individual preferred terms [PTs] and higher-level terms [HLTs]) have been considered ‘AEs of special interest’ (AESI) and ‘AEs of possible interest’ (AEPI) to the durvalumab program.

The AESIs reported in the AstraZeneca-sponsored durvalumab studies are defined as AEs with a likely inflammatory or immune-mediated pathophysiological basis resulting from the mechanism of action of durvalumab and requiring more frequent monitoring and/or interventions such as corticosteroids, immunosuppressants, and/or endocrine therapy. Endocrine therapies include standard endocrine supplementation, as well as treatment of symptoms resulting from endocrine disorders (eg, therapies for hyperthyroidism include beta blockers [eg, propranolol], calcium channel blockers [eg, verapamil, diltiazem], methimazole, propylthiouracil, and sodium perchlorate).

The AEPIs reported in the AstraZeneca-sponsored durvalumab studies are defined as AEs that could have a potential inflammatory or immune-mediated pathophysiological basis resulting from the mechanism of action of durvalumab but are more likely to have occurred due to other pathophysiological mechanisms, thus, the likelihood of the event being inflammatory or immune-mediated in nature is not high and/or is most often or usually explained by the other causes.

These AESIs and AEPIs are identified as a list of categories provided by the clinical team. Other categories may be added as necessary or existing terms may be merged. An AstraZeneca medically qualified expert, after consultation with the Global Patient Safety Physician, has reviewed the AEs of interest and identified which PTs contribute to each AESI/AEPI. A further review will take place prior to DBL to ensure any further terms not already included are captured within the categories.

Immune-mediated Adverse Events (imAE)

Durvalumab belongs to a class of drugs called immune checkpoint inhibitors. Because the mechanism of action of this class of drugs is to block the inhibitory signals that prevent T-cell activation, this drug may potentially cause imAEs.

Immune-mediated adverse drug reactions will be identified from both AESIs and AEPIs based on programmatic rules that consider interventions involving systemic steroid therapy, immunosuppressant use, and/or endocrine therapy (which, in the case of AEPIs, occurs after first considering an Investigator’s causality assessment and/or an Investigator’s designation of an event as immune-mediated). Infusion-related reactions and hypersensitivity/anaphylactic reactions are not considered imAE because they are common to monoclonal antibody drugs in general and occur due to a mechanism of action different than that for imAEs as defined in the imAE charter. Further details are provided in the imAE charter.

In addition, medical review of those AESI/AEPI may be performed to classify them as imAEs or not imAEs via an independent manual adjudication process.

3.3.5 Laboratory Data

Laboratory data will be collected throughout the study, from second screening to the second follow-up visit (12 weeks \pm 1 week after completion or discontinuation of study treatment i.e. durvalumab/placebo). Blood and urine samples for determination of hematology, clinical chemistry, and urinalysis will be collected as described in Section 8.2.1 of the CSP. For the definition of baseline and the derivation of post-baseline visit values considering visit window and how to handle multiple records, derivation rules as described in Section 4.1.2 will be used.

Change from baseline in hematology and clinical chemistry variables will be calculated for each postdose visit on-treatment. Common Terminology Criteria for Adverse Event (CTCAE) grades will be defined at each visit according to the CTCAE grade criteria using local or project ranges as required, after conversion of lab result to corresponding standard international (SI) units. The following parameters have CTCAE grades defined for both high and low values: Potassium, Sodium, Magnesium, and Corrected calcium.

Corrected calcium will be derived during creation of the reporting database using the following formula:

$$\text{Corrected calcium (mmol/L)} = \text{Total Calcium (mmol/L)} + ([40 - \text{Albumin (g/L)}] \times 0.02)$$

Creatinine clearance (CL) will be derived according to the Cockcroft-Gault formula (Cockcroft and Gault 1976).

Males:

$$\text{Creatinine CL (mL/min)} = \frac{\text{Weight (kg)} \times (140 - \text{Age at randomization})}{72 \times \text{serum creatinine (mg/dL)}}$$

Females:

$$\text{Creatinine CL (mL/min)} = \frac{\text{Weight (kg)} \times (140 - \text{Age at randomization})}{72 \times \text{serum creatinine (mg/dL)}} \times 0.85$$

Absolute values will be compared to the project reference range and classified as low (below range), normal (within range or on limits of range) and high (above range).

The maximum or minimum on-treatment value (depending on the direction of an adverse effect) will be defined for each laboratory parameter as the maximum (or minimum) post-baseline value at any time.

Local reference ranges will be used for the primary interpretation of laboratory data at the local laboratory. Project reference ranges will be used throughout for reporting purposes. The denominator used in laboratory summaries of CTCAE grades will only include evaluable patients, in other words those who had sufficient data to have the possibility of an abnormality.

For example:

- If a CTCAE criterion involves a change from baseline, evaluable patients would have both a baseline and at least 1 post-baseline (scheduled or unscheduled) value recorded.
- If a CTCAE criterion does not consider changes from baseline, to be evaluable the patient need only have at least 1 post-baseline (scheduled or unscheduled) value recorded.

3.3.6 Electrocardiograms

Resting 12-lead ECGs will be recorded at second screening and as clinically indicated throughout the study. Overall evaluation of ECG is collected in terms of normal or abnormal, and the relevance of the abnormality is termed as 'clinically significant' or 'not clinically significant'. Triplicate ECGs will be obtained in case of clinically significant ECG abnormalities.

At each time point the Investigator's assessment of the ECG will be collected locally. Heart rate, duration of QRS complex, RR, PR and QT intervals will be collected.

3.3.7 Vital Signs

Vital signs data will be collected throughout the study, from second screening to the first follow-up visit (4 weeks \pm 3 days after completion or discontinuation of study treatment, i.e. durvalumab/placebo).

3.4 CCI [REDACTED]

3.4.1 CCI [REDACTED]

CCI [REDACTED]

[REDACTED]

[REDACTED]

3.4.2 CCI [REDACTED]

CCI [REDACTED]

3.4.3 CCI [REDACTED]

CCI [REDACTED]

CCI [Redacted]

CCI [Redacted]

3.4.4 CCI [Redacted]

3.4.4.1 CCI [Redacted]

CCI [Redacted]

CCI [Redacted]

CCI [Redacted]

CCI [Redacted]

3.4.4.2 CCI [REDACTED]

CCI [REDACTED]

CCI [REDACTED]

CCI [REDACTED]

3.4.4.3 CCI [REDACTED]

CCI [REDACTED]

CCI [REDACTED]

4. ANALYSIS METHODS

Prior to CSP V2.0, a formal statistical analysis was to be performed to test the main hypotheses:

- H0: No difference between durvalumab and placebo
- H1: Difference between durvalumab and placebo

Under CSP V2.0 no formal statistical analyses will be performed, and all analyses will be exploratory. All data will either be summarized or listed only.

4.1 General Principles

The below mentioned general principles will be followed throughout the study:

- Descriptive statistics will be used for all variables, as appropriate, and will be presented by treatment group. Continuous variables will be summarized by the number of observations, mean, standard deviation, median, upper and lower quartiles, minimum, and maximum. For log-transformed data it is more appropriate to present geometric mean, coefficient of variation (CV), median, minimum and maximum. Categorical variables will be summarized by frequency counts and percentages for each category.
- Unless otherwise stated, percentages will be calculated out of the population total for the corresponding treatment group. Overall totals will be calculated for baseline summaries only.
- For continuous data, the mean, standard deviation, median and quartiles will be rounded to 1 additional decimal place compared to the original data. Minimum and maximum will be displayed with the same accuracy as the original data.
- For categorical data, percentages will be rounded to 1 decimal place, with the exception of 100% which will be presented as a whole number.
- SAS® version 9.4 or later will be used for all analyses.

4.1.1 Baseline

In general, for efficacy and PRO endpoints the last observed measurement prior to randomization will be considered the baseline measurement. However, for PRO endpoints, if an evaluable assessment is only available after randomization but before the first dose of study treatment then this assessment will be used as baseline. For safety endpoints the last observation before the first dose of study treatment will be considered the baseline measurement unless otherwise specified. For assessments on the day of first dose where time is not captured, a nominal pre-dose indicator, if available, will serve as sufficient evidence that the assessment occurred prior to first dose.

Assessments on the day of the first dose, where neither time nor a nominal pre-dose indicator are captured, will be considered prior to the first dose if such procedures are required by the protocol to be conducted before the first dose.

If two visits are equally eligible to assess patient status at baseline (e.g. screening and baseline assessments both on the same date prior to first dose with no washout or other intervention in

the screening period), the average can be taken as a baseline value. For non-numeric laboratory tests (i.e. some of the urinalysis parameters) where taking an average is not possible the best value would be taken as baseline as this is the most conservative. In the scenario where there are two assessments on day 1, one with time recorded and the other without time recorded, the one with time recorded would be selected as baseline. Where safety data are summarized over time, study day will be calculated in relation to date of first study treatment.

In all summaries, change from baseline variables will be calculated as the post-treatment value minus the value at baseline. The percentage change from baseline will be calculated as $(\text{post-baseline value} - \text{baseline value}) / \text{baseline value} \times 100$.

4.1.2 General Considerations for Safety and PRO Assessments

The following conventions will apply for visit windows on safety and ePRO:

- The time windows will be exhaustive so that data recorded at any time point has the potential to be summarized. Inclusion within the time window will be based on the actual date and not the intended date of the visit.
- All unscheduled visit data have the potential to be included in the summaries.
- The window for the visits following baseline will be constructed in such a way that the upper limit of the interval falls half way between the 2 visits (the lower limit of the first post-baseline visit will be Day 2). If an even number of days exists between 2 consecutive visits then the upper limit will be taken as the midpoint value minus 1 day. An example is provided in Appendix A.
- For summaries showing the maximum or minimum values, the maximum/minimum value recorded on-treatment will be used (regardless of where it falls in an interval).
- Listings should display all values contributing to a time point for a patient.
- For visit windows with more than one record
 - If there is more than one value per patient within a time window then the closest value to the scheduled visit date will be summarized, or the earlier, in the event the values are equidistant from the nominal visit date. If there are two values recorded on the same day and CTCAE grades are available then the record with the highest toxicity grade should be used. Alternatively, if there are two records recorded on the same day and the toxicity grade is the same (or is not calculated for the parameter) then the average of the two records should be used. The listings will highlight the value for the patient that contributed to the summary table, wherever feasible. Note: in summaries of extreme values all post-baseline values collected are used including those collected at unscheduled visits regardless of whether or not the value is closest to the scheduled visit date.

- For summaries at a patient level, all values will be included, regardless of whether they appear in a corresponding visit-based summary, when deriving a patient level statistic such as a maximum.

Imputation Rules

Missing safety data will generally not be imputed. However, safety assessment values of the form of '< x' (i.e. below the lower limit of quantification) or '> x' (i.e. above the upper limit of quantification) will be imputed as 'x' in the calculation of summary statistics but displayed as '< x' or '> x' in the listings. Additionally, AEs that have missing causality (after data querying) will be assumed to be related to durvalumab or placebo.

For the handling of partial date of birth and missing/partial start and/or stop dates of AEs, medications/therapies, deaths and subsequent anti-cancer therapies (including radiotherapy), refer to Appendix B.

The original incomplete or missing dates will be presented in the listings.

All AEs will be considered as treatment-emergent unless the opposite can be clearly stated. Imputation will be done only in the context of identifying TEAEs.

All medications/therapies will be considered as concomitant unless the opposite can be clearly stated.

4.2 Analysis Methods

Only descriptive summaries or listings will be produced. The following table (Table 5) details the statistical analysis. Where listings are specified, these will be produced on the FAS only and will include the PD-L1 TC \geq 1% analysis set status.

Table 5 Statistical Analyses to be Conducted

Endpoints	Notes
Disease-free survival (DFS)	Primary analysis using descriptive summaries based on Investigator assessments (RECIST 1.1) for the FAS. Listing only for PD-L1 \geq 1% analysis set.
Overall survival (OS)	Listing only.
Progression-free survival (PFS)	Listing only.
CCI	CCI

Endpoints	Notes
CCI [REDACTED]	CCI [REDACTED]
Change from baseline in PRO endpoints CCI [REDACTED]	Listing only.
Time to deterioration CCI [REDACTED]	Listing only.
DFS Disease-free survival; CCI [REDACTED]; CCI [REDACTED]; FAS Full analysis set; OS Overall survival; PFS Progression-free survival; CCI [REDACTED]; RECIST Response Evaluation Criteria in Solid Tumors.	

4.2.1 Multiplicity

Under CSP V2.0, no methods for multiplicity control will be performed and the analyses of all endpoints will be considered exploratory.

4.2.2 Disease-Free Survival (DFS)

4.2.2.1 Primary Analysis of DFS

Disease-free survival, using Investigator assessment according to RECIST 1.1, will be summarized, for the FAS. This will include the number (%) of patients with event or censored, along with the reason for event/censoring. Kaplan-meier curves will also be produced.

DFS data on the PD-L1 $\geq 1\%$ analysis set will be listed only.

Supportive Summaries

Additionally, a summary of time to MRD+ emergence during surveillance may be provided and this may also be included in the DFS supportive listing.

The location of the disease recurrence (local/regional, distant or second primary NSCLC) will be summarized by treatment group.

Additionally, summary statistics will be presented for the number of days from censoring to DCO for all censored patients. A summary of the duration of follow-up will be summarized using time from randomization to date of censoring (date last known to have not had disease

recurrence or died) in censored patients only (patients who have not had disease recurrence or died), presented by treatment group.

A summary table of first subsequent cancer therapies relative to recurrence by treatment group will be provided.

All the collected RECIST 1.1 data will be listed.

4.2.2.2 Subgroup Analyses

No subgroup analyses will be performed.

4.2.3 Overall Survival (OS)

Overall survival will be listed only, for the FAS.

4.2.4 CCI [REDACTED]

CCI [REDACTED]

4.2.5 CCI [REDACTED]

CCI [REDACTED]

4.2.6 Data Cut-Offs

Following implementation of CSP V2.0, the DCO will occur after the last patient has either discontinued the study or has signed consent (ICF3) to receive open-label durvalumab, whichever occurs later. This will be followed by DBL and the primary DFS analysis. The study will then be concluded.

Details regarding the approach used for removing post-DCO data from SAS datasets can be found in the AstraZeneca Oncology Guidance on Data Cut-off Processing and Clean file/DBL Considerations document as well as the DCO Specifications for this study.

4.2.7 CCI [REDACTED]

CCI [REDACTED]

- CCI [REDACTED]

- CCI [REDACTED]

- CCI [REDACTED]

- CCI

4.2.8 CCI

CCI

4.2.9 Safety

Safety and tolerability data from all cycles of treatment will be combined. The safety analysis set will be used for reporting of safety according to actual treatment group as defined in Section 2.1.3.

4.2.9.1 Adverse Events (AEs)

All AEs, both in terms of current MedDRA PT and CTCAE grade, will be summarized descriptively by count (n) and percentage (%) for each treatment group. Any AE occurring before study treatment (i.e. before the administration of the first dose of durvalumab/placebo) will be included in the AE listings, but will not be included in the summary tables (unless otherwise stated). These will be referred to as ‘pre-treatment’. However, any AE occurring before the administration of the first dose of study treatment on study day 1 that increases in severity after the first dose will be regarded as treatment-emergent and thus will be included in the majority of summary tables.

Adverse events observed up until 90 days following discontinuation of study treatment (i.e. the last dose of durvalumab/placebo) or until the initiation of the first subsequent anti-cancer therapy (including radiotherapy, except for palliative radiotherapy) following discontinuation of study treatment (whichever occurs first) will be used for the reporting of the AE summary tables. This will more accurately depict AEs attributable to study treatment only, as a number of AEs up to 90 days following discontinuation of study treatment are likely to be attributable to subsequent therapy.

Any AEs that occur between the start of subsequent anti-cancer therapy and up until 90 days following discontinuation of study treatment will be flagged in the data listings.

All reported AEs will be listed along with the date of onset, date of resolution (if AE is resolved) and Investigator’s assessment of severity and relationship to durvalumab/placebo. Frequencies and percentages of patients reporting each PT will be presented (i.e. multiple events per patient will not be accounted for apart from on the episode level summaries).

Summary information (the number and percentage of patients by system organ class (SOC) and PT separated by treatment group) will be tabulated for:

- All AEs

- All AEs possibly related to study treatment (as determined by the reporting Investigator)
- AEs with maximum CTCAE grade 3 or 4
- AEs with maximum CTCAE grade 3 or 4, possibly related to study treatment (as determined by the reporting Investigator)
- SAEs with outcome of death
- SAEs with outcome of death possibly related to study treatment (as determined by the reporting Investigator)
- All SAEs
- All SAEs possibly related to study treatment (as determined by the reporting Investigator)
- AEs leading to discontinuation of study treatment
- AEs leading to discontinuation of study treatment, possibly related to study treatment (as determined by the reporting Investigator)
- AEs leading to dose interruption of study treatment

An overall summary of the number and percentage of patients in each category will be presented, as well as an overall summary of the number of episodes in each category. Summaries of the number and percentage of patients with AEs will be provided by maximum reported CTCAE grade, SOC, PT and treatment group. In addition, a truncated AE table of most common AEs and another table showing most common AEs with maximum CTCAE grade 3 or 4, showing all events that occur in at least 5% of patients overall will be summarized by PT, by decreasing frequency in the total column (the total column will not be displayed in the AE tables). This cut-off may be modified after review of the data. When applying a cut-off (i.e. $x\%$), the raw percentage should be compared to the cut-off, no rounding should be applied first (i.e. an AE with frequency of 4.9% will not appear if a cut-off is 5%).

In addition, all AEs will be listed (including listings for AEs that required treatment with steroids, immunosuppressants, or endocrine treatment, grade changes for AEs of CTCAE grade ≥ 3 , and grade changes for AEs of CTCAE grade ≥ 3 that required treatment with steroids, immunosuppressants, or endocrine treatment). Listings of key patient information for SAEs, and AEs leading to discontinuation of durvalumab/placebo or SoC will also be provided.

Deaths

A summary of all deaths will be provided with number and percentage of patients in the FAS by treatment group, categorized as:

- Total number of deaths (regardless of date of death)

- Death related to disease under investigation only, as determined by the Investigator
- Death related to disease under investigation and an SAE with outcome of death
 - (a) AE onset prior to subsequent anti-cancer therapy, defined as an AE with onset date (or pre-treatment AEs that increase in severity) on or after the date of first dose of study treatment and up to and including the earlier of 90 days following the date of last dose of study treatment or the date of initiation of the first subsequent anti-cancer therapy
 - (b) AE onset after start of subsequent anti-cancer therapy, defined as an AE with onset date more than 90 days following the date of last dose of study treatment or after the date of initiation of the first subsequent anti-cancer therapy (whichever occurs first)
- SAE with outcome of death only
 - (a) AE onset prior to subsequent anti-cancer therapy, defined as an AE with onset date (or pre-treatment AEs that increase in severity) on or after the date of first dose of study treatment and up to and including the earlier of 90 days following the date of last dose of study treatment or the date of initiation of the first subsequent anti-cancer therapy
 - (b) AE onset after start of subsequent anti-cancer therapy, defined as an AE with onset date more than 90 days following the date of last dose of study treatment or after the date of initiation of the first subsequent anti-cancer therapy (whichever occurs first)
- Death after end of safety follow-up period (last dose of study treatment [durvalumab/placebo] + 90 days) and not due to disease under investigation
- Unknown reason for death
- Other deaths

All deaths will be listed along with time from first and last dose, primary and secondary causes, and relationship to disease using the FAS.

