### **9.4.2 Calculation or derivation of safety variables**

#### **9.4.2.1 Adverse events**

Safety and tolerability will be assessed in terms of AEs (including SAEs), deaths, laboratory data, vital signs, ECGs, and exposure. These will be collected for all patients. Data from all cycles of treatment will be combined in the presentation of safety data. “On

treatment” will be defined as assessments between date of start dose and 90 days following discontinuation of IP (ie, the last dose of durvalumab/placebo). For AEs, on treatment (or treatment-emergent AEs) will be defined as any AEs that started after dosing or prior to dosing and which worsens following exposure to the treatment.

The SAS will be used for reporting of safety data.

Adverse events observed up until 90 days following discontinuation of the last dose of durvalumab/placebo or until the initiation of the first subsequent therapy following discontinuation of treatment (whichever occurs first) will be used for the reporting of the AE summary tables. This will more accurately depict AEs attributable to study treatment only as a number of AEs up to 90 days following discontinuation of durvalumab/placebo are likely to be attributable to subsequent therapy. However, to assess the longer-term toxicity profile, AE summaries will also be produced containing AEs observed up until 90 days following discontinuation of durvalumab/placebo (ie, without taking subsequent therapy into account). Any events in this period that occur after a patient has received further therapy for cancer (following discontinuation of study treatment) will be flagged in the data listings.

A separate data listing of AEs occurring more than 90 days after discontinuation of IP will be produced. These events will not be included in AE summaries.

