6. CHANGES OF ANALYSIS FROM PROTOCOL

The following are changes from the planned analyses described in version 2 of the CSP.

Overall visit response table updated to more accurately reflect RECIST 1.1 evaluations and responses applicable to this study.

Except that change, this SAP has been produced in line with section 10.4 of CSP V2.0, which states:

“Under CSP v2.0, as a result of the decision by AstraZeneca to close enrollment to the study and end study assessments early, all analyses of the objectives and endpoints listed in Section 3 will be descriptive only and considered exploratory. Further details will be included in the SAP.”

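### SAP v2.0 omits, without declaring it, the full 90-day AE summaries that CSP 9.4.2.1 still promises, so non-fatal AEs after next-line therapy are listed but not counted by arm in the AE, SAE and AESI tables

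*SAP*

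**What the plan says.** CSP v2.0 section 9.4.2.1 describes two sets of AE summaries. The main set is capped at 90 days after the last dose, and AEs "until the initiation of the first subsequent therapy following discontinuation of treatment (whichever occurs first) will be used for the reporting of the AE summary". For the longer-term toxicity profile, it adds that "AE summaries will also be produced containing AEs observed up until 90 days following discontinuation of durvalumab/placebo (ie, without taking subsequent therapy into account"). The same section defines the on-treatment period as first dose to 90 days after last dose, with no cut at later therapy. It also asks for events after further cancer therapy to be flagged in the listings, in addition to the second set of summaries.

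SAP v2.0 section 3.3 ends the on-treatment period at 90 days or "up to and including the date of initiation of the first subsequent anti-cancer therapy", whichever is earlier. Palliative radiotherapy does not end it. This is the default for all safety summaries; treatment-emergent AEs (3.3.4) depend on it, and 4.2.9.1 and 4.2.9.3 restate the cut for AE tables and laboratory reporting. For AEs that begin once subsequent anti-cancer therapy has started, 4.2.9.1 says that those "up until 90 days following discontinuation of study treatment will be flagged in the data listings". It also says: "All reported AEs will be listed along with the date of onset, date of resolution (if AE is resolved) and Investigator’s assessment of severity"; relationship to study treatment is listed too.

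SAP Section 1 says that changes to CSP specifications will be described in SAP Section 6. That section names one change, to the overall visit response table, and continues: "Except that change, this SAP has been produced in line with section 10.4 of CSP V2.0".

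**The concern.** The CSP and SAP disagree on which safety tables will exist, and the section meant to reconcile them does not mention it. This matters because safety is the only remaining secondary objective (CSP Table 7, SAP 1.1.2).

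The date on which a patient starts another anti-cancer therapy is a post-randomization event that may follow from recurrence. If its timing differs between arms, the truncated AE window differs in length between arms. The CSP's second set is the check on this, because its window does not depend on what the patient received next. Without it, a reader of the tables cannot see whether the by-arm picture changes over the full 90 days. For example, a non-fatal SAE 60 days after last dose, in a patient who began chemotherapy at day 35, would be listed and flagged but would not be counted in the AE or SAE tables.

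**Working it through.** The CSP and SAP give no figure to reproduce here. The check is a comparison of text, with two small calculations for scale.

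1. **Is the second set still planned in the CSP?** Section 9.4.2.1 of v2.0 retains it. The v2.0 note at the head of Section 9 makes all analyses descriptive and names two analyses as dropped: interim and medical resource use. Section 10.4 repeats that analyses are descriptive and leaves details to the SAP. Neither withdraws the second set, and a further descriptive table is consistent with both.

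2. **Does the SAP contain it?** No. SAP 4.2.9.1 has the truncated set only. The SAP amendment history records that v2.0 removed the longer-term toxicity profile summaries, so the removal was deliberate.

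3. **Is it declared as a change from the CSP?** No. Section 6 names only the visit response table. It does not mention the on-treatment definition either, although the CSP and SAP definitions differ.

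4. **Where does an AE go if it starts after first subsequent anti-cancer therapy and within 90 days of last dose?**
   - Non-fatal AE: listed, with causality, and flagged. It is not counted in the 4.2.9.1 tables. It is not counted in the AESI/AEPI tables of 4.2.9.2 either, since the SAP 3.3 default applies unless otherwise specified.
   - imAE: summarized in a similar manner, but details are in a charter not seen, so the window cannot be confirmed.
   - Fatal SAE: counted by arm in the Deaths summary, category (b). That category also takes onset more than 90 days after last dose, so it does not reproduce the 90-day view.
   - After palliative radiotherapy only: still in the tables.

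5. **Scale per patient.** SAP 1.2 expects about 30 randomized patients at 1:1. Assuming equal arms, all treated: 30 / 2 = 15 per arm, and 1 / 15 = 6.7%.

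6. **Share of one affected patient's window.** The documents do not give the time from last dose to next-line therapy. Assuming 28, 42 or 56 days, the excluded part of the 90 days is (90 − 28)/90 = 69%, (90 − 42)/90 = 53% or (90 − 56)/90 = 38%. This says nothing about how many patients or AEs are affected, which cannot be derived.

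**The case against.** The strongest reply is that this is deliberate scaling down of a study that closed early. CSP 9.5.2 leaves the safety summaries to be defined in the SAP, and 10.4 leaves further details there. CSP Section 10 is the reference point after v2.0, with older text kept for study history. The SAP amendment history states the removal openly. Other content was cut in the same way without appearing in Section 6: OS became a listing (4.2.3) and subgroup analyses went (4.2.2.2). With about 15 patients per arm, a flagged listing can be read case by case, and there are further listings for SAEs, AESI/AEPI and AEs needing steroids, immunosuppressants or endocrine treatment.

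A second reply is that the full window will often not exist. Under CSP 10.2 and 10.3, patients are discontinued or offered open-label durvalumab at closure. After that move AEs are collected but only SAEs are reported, and the data cut-off follows the last discontinuation or ICF3 signature.

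Much of this stands. The effect is small, the removal is not a selective safety cut, and the full-window table would be incomplete for some patients. It does not reconcile the documents. The amendment history logs changes between SAP versions, not departures from the CSP. Leaving details to the SAP is not the same as withdrawing summaries that the CSP says will be produced. Listings give no counts by arm, and the CSP asked for the flag as well as the tables.

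**Conclusion.** The point holds as an undeclared departure from CSP 9.4.2.1: a by-arm safety summary is missing and the on-treatment definition is narrower. The consequence is limited to non-fatal AEs that start after first subsequent anti-cancer therapy (other than palliative radiotherapy) and within 90 days of last dose. The scale of 6.7% per patient rests on about 30 randomized patients in equal arms, all treated.

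Four stronger readings are tempting, and the documents do not support them.
- That late toxicity is lost or appears in no table. These AEs are listed with causality and flagged, and fatal SAEs are in the Deaths table.
- That patients who recur drop out of the tables. Recurrence alone does not close the window.
- That the truncated window is itself a SAP error. The CSP uses the same kind of cut for its main AE tables, on the ground that later AEs are likely to be due to the next therapy.
- That most patients are affected. The design assumptions for DFS in CSP 9.2 (placebo median 4 months, HR 0.63) give event rates by 12 months of 1 − 0.5^(12/4) = 87.5% on placebo and 1 − 0.125^0.63 = 73.0% on durvalumab. These belong to the 284-patient design and concern DFS events. They do not give how often, or how soon after last dose, another therapy starts.

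**What to change.** Add one overall AE summary table by arm, with rows for any AE, maximum grade 3-4, SAE and AESI/imAE. Count from first dose to last dose plus 90 days, or to data cut-off or end of data collection if earlier, regardless of subsequent therapy. Show it beside the truncated version. In SAP Section 6, declare the narrower on-treatment definition of 3.3 and the removal of the other full-window tables, with reasons.

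The cost is one extra table from data already collected and flagged, and a short paragraph. Some AEs in the full-window column will be due to the next therapy, which the paired display makes visible. The window will be incomplete for patients discontinued or moved to open-label treatment at closure, and a footnote should say so.
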